- *Baseline Day -1 Prophylactic Prednisolone and placebo administration:* In an attempt to dampen the host immune response to the adeno-associated virus (AAV) derived therapy, participants randomized to the treatment arm will receive oral prophylactic prednisolone **CCI** [REDACTED] Participants randomized to the sham procedure arm will receive a matching placebo. Treatment or placebo will continue for **CCI** [REDACTED]
- **Treatment Period 1**
 - *OAV101 treatment or sham procedure (Day 1, Day 2, optional Day 3):* Participants will be admitted to the study center on Day 1 (or on Day -1 as per local standard of care). Participants randomized to the treatment cohort will receive intrathecal OAV101. Participants randomized to the control group will receive a sham procedure that consists of only a needle prick. **CCI** [REDACTED] in accordance with the Assessment Schedule ([Table 8-1](#)). Lumbar puncture and OAV101 administration should be performed using an atraumatic spinal needle (e.g. Whitacre, 22 or 25 gauge) which significantly lowers the incidence of blood patch treatment ([Hatfield et al 2008](#)). Following the OAV101 administration/sham procedure on Study Day 1, participants will remain at the study center for 24 to 48 hours for post-procedure for safety monitoring.
- **Follow-up Period 1**
 - *Visit Week 1 to Visit Week 12:* Assessments proceed as outlined in [Table 8-1](#).
 - *Visit Week 16 to Visit Week 48:* Assessments proceed as outlined in [Table 8-1](#).
 - *End of Follow-up Period 1 (Week 52):* Participants complete End of Follow-up Period 1 (Week 52) when each participant returns to the treatment center for final follow-up evaluations as per the Assessment Schedule ([Table 8-1](#)).
 - Blinding will be maintained through the end of study (Week 64). When all participants complete the Week 52 visit, all data collected through Week 52 will be analyzed (Primary analysis). Data will be reported in a Registration Clinical Study Report (CSR) for health authority data submission. *See Treatment Period 2 description for further discussion of implications of elevated anti-AAV9 antibodies for trial blinding.*
 - To minimize the time that the control group is untreated ([Section 4.2](#)), participants will be assessed for eligibility to enter Treatment Period 2 at the Follow-up Period 1 Week 48 visit. Eligible participants will begin Treatment Period 2 (Week 52 +1 day visit) immediately after completion of Follow-up Period 1.

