12.5.2 Safety endpoints

For all safety analyses, the Safety Set will be used. All listings and tables will be presented by treatment group.

Safety summaries (tables, figures) will include only data from the post-treatment period with the exception of baseline data, which will also be summarized where appropriate (e.g., change from baseline summaries). In addition, a separate summary for deaths occurring post-treatment will be provided. In particular, summary tables for adverse events (AEs) will summarize only on-treatment events, with a start date on or after the date of dose administration (treatmentemergent AEs).

The on-treatment period lasts from the date of administration of study treatment to completion of the study at Week 64.

Adverse events

All information obtained on adverse events will be listed by treatment group and participant.

The number (and percentage) of participants with treatment emergent adverse events (events with an onset after the dose of study medication or events which were present prior to start of double-blind treatment but increased in severity, changed from being not suspected to being suspected of study drug relationship, or developed into SAEs after the start of the treatment period) will be summarized in the following ways:

- by treatment group, primary system organ class and preferred term.
- by treatment group, primary system organ class, preferred term and maximum severity.

- by treatment group, Standardized MedDRA Query (SMQ) and preferred term.

Separate summaries will be provided for study medication related adverse events, deaths, serious adverse events, and other significant adverse events leading to discontinuation.

The number (and proportion) of participants with AESIs will be summarized by treatment.

A participant with multiple adverse events within a primary system organ class is only counted once towards the total of the primary system organ class.

Vital signs

All vital signs data will be summarized by treatment and visit/time.

12-lead ECG

All ECG data will be summarized by treatment and visit/time.

PR, QRS, QT, QTcF, and RR intervals will be obtained from 12-lead ECGs for each participant during the study.

Categorical analysis of QT/QTc interval data based on the number of participants meeting or exceeding predefined limits in terms of absolute QT/QTc intervals or changes from Baseline will be presented.

Echocardiogram

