2.1.1 General definitions

Study treatment is OAV101 (1.2x10¹⁴ vector genomes) or sham administration.

The **date of first administration of study treatment** is defined as the date of OAV101/sham administration during Treatment Period 1.

The **date of second administration of study treatment** is defined as the date of OAV101/sham administration during Treatment Period 2.

Study day is the number of days since the date of first administration of study treatment for period 1 and number of days since the date of second administration of study treatment for period 2.

- Study day 1 is the date of the first administration of study treatment during Treatment Period 1 and the date of second administration of study treatment during Treatment Period 2 .
- Study day of date X = date X – date of first administration of study treatment during Treatment Period 1 + 1 if date X is on or after the date of first administration of study treatment during Treatment Period 1.
- Study day of date X = date X – date of first administration of study treatment during Treatment Period 1 if date X is before the date of first administration of study treatment during Treatment Period 1. Study days before the first study treatment administration during Treatment Period 1 will have the prefix “-”.

Baseline is defined as follows:

- **HFMSE**: Baseline value for HFMSE (i.e., total or individual item) score is defined as the average of HFMSE (i.e., total or individual item) score used for stratification (maximum of all available values before baseline visit) and the measurement or evaluation made at the baseline visit prior to the first administration of study treatment during Treatment Period 1, assuming both values have complete and valid scores available. If just one of the above mentioned values (score used for stratification and baseline visit measurement) has a complete and valid score available, then the baseline HFMSE (i.e., total or individual item) score is defined as the single available value.

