- **RULM**: Baseline value for RULM total score is defined as the average of all non-missing assessments prior to the first administration of study treatment during Treatment Period 1, assuming all assessments have complete and valid total scores available. If two of the assessments have a complete and valid total score available, then the baseline RULM total score is defined as average of the two available assessment scores. If just one of the assessments has a complete and valid total score available, then the baseline RULM total score is defined as the single total score available.
- **Other assessments**: The latest non-missing measurement or evaluation made prior to the first administration of study treatment during Treatment Period 1.

Change from baseline is defined as post-baseline value minus baseline value.

For HFMSE and RULM, the **End of Follow-up Period 1** assessment is defined as the average of the Week 48 and Week 52 assessments, assuming both assessments have complete and valid total / individual scores available. If just one of the assessments collected at these two visits has a complete and valid total / individual score available, then the end of Follow-up Period 1

assessment is defined as the single assessment total / individual score collected at Week 48 or Week 52.

Last participation day can be calculated using end of participation date – date of second administration of study treatment + 1.

Inexact values will be handled as follows.

- If a laboratory value is recorded/reported as “>X”, “≥X”, “- If an antibody titer value is reported as <12.5, a value of 0.5×12.5 will be used and if ≥ 819200 is reported, a value of 1.5×819200 will be used for analysis purposes. The originally recorded values will be displayed in corresponding listings.

An **Adverse Event** (AE) is any untoward medical occurrence in a clinical investigation participant, which does not necessarily have a causal relationship with the drug or device under study.

A Treatment Emergent Adverse Event (TEAE) is any AE whose onset or worsening occurred after dosing on Day 1 till the end of follow-up period 2.

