2.4 Treatments (study treatment, rescue medication, concomitant therapies, compliance)

2.4.1 Study treatment / compliance

The following details pertaining to treatment administration will be summarized using descriptive statistics by age subgroup (≥ 2 to < 5 years, ≥ 5 to < 18 years) and overall (≥ 2 to < 18 years). Separate summary tables will be produced for Treatment Period 1 using the SAF and for Treatment Period 2 using the ATP2 population:

- Anatomical location of administration (L2-L3, L3-L4, L4-L5, L5-S1)
- Number and percentage of participants taking prednisolone/placebo 24 hours prior to injection
- Number and percentage of participants with dose interruption and their corresponding reason
- Treatment compliance (%) if the dose is not fully completed. Treatment compliance is defined as 100 times the dose administered divided by the planned dose. Planned dose is 3ml, equivalent to 1.2×10^{14} vector genomes.

A listing of treatment administration during both Treatment Periods will be produced.

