2.7.1 Adverse events (AEs)

An overview summary table of AEs reported through the end of Follow-up Period 1 will be presented by Treatment Period 1 treatment group (OAV101, sham), consisting of the number and percentage of participants experiencing at least one event for each of the following categories:

- Any TEAE
- Any TEAE related to study treatment
- Any serious TEAE
- Any serious TEAE related to study treatment
- Any severe TEAE
- Any TEAE leading to discontinuation from study
- Any TEAE leading to death
- Any AESI (refer to [Section 2.7.1.1](#) of this SAP)

The number and percentage of participants with TEAEs will be summarized in the following ways:

- by treatment group, primary SOC, and PT along with the total number of events
- by treatment group, primary SOC, PT, and maximum severity

Separate summaries by Treatment Period 1 treatment group (OAV101, sham), primary SOC, and PT will be provided for TEAEs leading to death, TEAEs related to study treatment, TEAEs related to prednisolone/placebo, serious TEAEs, serious TEAEs related to study treatment, TEAEs leading to discontinuation from study, non-serious TEAEs reported in >5% of participants, and AESIs.

Additionally, separate summaries by Treatment Period 1 treatment group (OAV101, sham) and PT will be provided for TEAEs, TEAEs related to study treatment and serious TEAEs.

All information obtained on AEs through the end of study will be listed by Treatment Period 1 treatment group (OAV101, sham) and participant.

The number and percentage of participants with TEAEs reported within 72 hours of treatment with the study treatment will be summarized by treatment group, primary SOC and PT.

A similar, second set of outputs will be produced to summarize the TEAEs reported after dosing with OAV101 and through the end of Follow-up Period 2 using OAS. In this second set of outputs, only TEAEs reported on/after OAV101 dosing (during Treatment Period 1 and through the end of study for participants originally randomized to OAV101, during Treatment Period 2 and through the end of study for participants originally randomized to sham administration) will be considered.

For the legal requirements of ClinicalTrials.gov and EudraCT, two required tables on TEAEs which are not serious adverse events with an incidence > 5% and on treatment emergent serious

adverse events and SAE suspected to be related to study treatment will be provided by system organ class and preferred term based on the SAF.

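### Treatment-emergent AEs are counted from the Day 1 procedure, but prednisolone/placebo starts about a day earlier, so the prednisolone/placebo-related table omits its own lead-in and the vital-sign baseline is on steroid in one arm only

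*SAP*

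**What the plan says.** **Steroid lead-in.** Protocol Section 3 describes the first dose under the heading "Baseline Day -1 Prophylactic Prednisolone and placebo administration". The OAV101 arm takes prednisolone, and "Participants randomized to the sham procedure arm will receive a matching placebo". The exact timing is redacted. SAP 2.4.1 supports a lead-in of about a day by planning to report "Number and percentage of participants taking prednisolone/placebo 24 hours prior to injection".

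**Safety clock.** SAP 2.1.1 limits study treatment to OAV101 or sham. Its first administration date is "defined as the date of OAV101/sham administration during Treatment Period 1". A TEAE is "any AE whose onset or worsening occurred after dosing on Day 1 till the end of follow-up period 2". SAP 2.7 starts the on-treatment period at the same administration. Protocol 12.5.2 uses a date rule instead: its AE tables "will summarize only on-treatment events, with a start date on or after the date of dose administration".

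**Steroid-related output.** SAP 2.7.1 plans a separate table, by system organ class and preferred term, of "TEAEs related to prednisolone/placebo".

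**Baseline.** For assessments other than HFMSE and RULM, SAP 2.1.1 takes "The latest non-missing measurement or evaluation made prior to the first administration of study treatment during Treatment Period 1". Nothing requires that value to come before the first prednisolone/placebo dose.

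**The concern.** The blinded regimen has two parts, and the safety definitions are tied only to the second. For the main comparison of OAV101 with sham that is a reasonable choice. For a table meant to describe events related to prednisolone/placebo it is not, because counting starts about a day after the exposure does. The omission also differs by arm in what it hides: active steroid in the OAV101 arm and placebo in the sham arm.

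The baseline issue has the same source. Protocol 4.5.3 names raised blood pressure as a corticosteroid risk, and SAP 2.7.4.2 summarises change from baseline in systolic and diastolic pressure. If the first dose has already moved blood pressure before the procedure, that movement is built into the OAV101 baseline and not into the sham baseline.

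**Working it through.** The plan gives no figure on this point, so the check sets dates and rules side by side.

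**1. Length of the gap.** Under the study-day rule in SAP 2.1.1 there is no Day 0, so Day -1 is the calendar day before Day 1. The lead-in is about 1 day, which agrees with the 24-hour item in SAP 2.4.1.

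**2. What happens to an AE that starts in the lead-in.**

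| Course of the event | TEAE under SAP 2.1.1 | In the prednisolone/placebo-related table | In the AE listing |
|---|---|---|---|
| Worsens after the procedure | Yes | Yes, if judged related | Yes |
| Does not worsen after the procedure | No | No | Yes |

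Only the second row is a gap. Protocol 10.1.1 collects AEs from consent, and SAP 2.7.1 lists all AE information through end of study, so the data exist.

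**3. Size of the AE gap.** With the planned arm sizes, the uncovered exposure is at most 75 × 1 = 75 child-days on prednisolone and 50 × 1 = 50 child-days on placebo. Per child this is 1/(52 × 7) = 1/364, about 0.3% of Period 1.

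**4. Which baselines follow the steroid start.**

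| Assessment | Last scheduled pre-procedure value | After the first prednisolone/placebo dose? |
|---|---|---|
| Vital signs, including blood pressure | Day 1, pre-dose (Protocol 8.4.4) | Yes |
| Troponin I | Screening Visit 1 (Table 8-1) | No |
| Urinalysis, coagulation | Baseline visit, Day -1 (Table 8-1) | Depends on order within Day -1, not visible |
| Hematology, chemistry, liver tests | Rows not visible | Cannot be determined |
| HFMSE, RULM | Averages under their own rule | The latest-value rule does not apply |

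So the documents establish the point for vital signs only. This assumes that the pre-dose reading on Day 1 is treated as before the procedure by clock time.

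**5. Direction of the vital-sign effect.** Let b be a child's pre-steroid value, y a later value, and d the mean effect of the lead-in prednisolone on the Day 1 pre-dose reading. The reported change is y − (b + d) = (y − b) − d in the OAV101 arm and y − b in the sham arm. The between-arm difference in mean change is therefore shifted by −d at every visit. The documents give no value for d.

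**6. Outputs that the shift does not reach.** The high and low blood-pressure flags in SAP 5.6 use absolute limits, and SAP 2.7.4.2 also summarises observed values at each visit. The liver elevation criteria in SAP 2.7.3 ignore the baseline value, and low cardiac function in SAP 2.7.4.1 uses fixed cut-offs.

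**7. Crossovers.** Protocol 4.3 says the same prednisolone/placebo administration is followed in Period 2, but the timing before the Week 52 + 1 Day procedure is redacted in Section 3. The Period 1 windows for vital signs, hematology and chemistry in SAP 2.1.2 run to the day before that procedure, and the post-OAV101 outputs start at the OAV101 dose. If the first Period 2 dose precedes the procedure, values from that day can fall in Week 52 of the sham arm. The ceiling is 50 child-days, or 50 − 5 = 45 if the protocol's estimate of up to 5 antibody-ineligible controls is fully realised.

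**8. Day 1 itself.** An event on Day 1 before the injection, for instance under sedation, meets the date rule in Protocol 12.5.2 but not the SAP's condition that onset or worsening follow dosing. The two wordings can classify the same event differently.

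**The case against.** The strongest reply is that the anchor is deliberate and sound. Protocol 6.1 and SAP 2.1.1 both define study treatment as OAV101 or sham, and the safety objective compares those two. Moving the TEAE start for every table would add events from before the vector was given, and replacing the baseline throughout would discard the value closest to the procedure. That stands, and it is why the fix is confined to the outputs about the steroid.

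Two further points also stand. The exact first-dose time is redacted, so Day -1 rests on a heading and one SAP item. The exposure at issue is about one day.

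The reply does not rescue the prednisolone/placebo-related table, which still leaves out the start of the exposure named in its title.

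A reader might go further and infer any of the following, which the documents do not support:

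- **That lead-in events are lost.** They are recorded from consent and listed, and those that worsen after the procedure are counted.
- **That the whole OAV101 safety baseline is on steroid.** The legible schedule shows otherwise for troponin I and leaves the laboratory tests undetermined.
- **That Period 2 steroid events are certainly credited to sham.** This depends on redacted timing.
- **That sedation events before the injection are excluded.** They meet the protocol's date rule, so the issue there is inconsistent wording.

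**Conclusion.** The point holds as a limited reporting defect. The prednisolone/placebo-related table is incomplete by design for non-worsening events in a lead-in of about one day, and what it omits differs by arm. The vital-sign change-from-baseline summaries mix a steroid-exposed baseline with a placebo-exposed one. Both rest on the assumption that the first dose is taken at about Day -1, as the visible text indicates.

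The size is bounded by about 75 prednisolone child-days in Period 1. The bias in blood-pressure change equals whatever effect that lead-in has by the Day 1 reading, which the documents do not quantify. It is probably small. A conclusion that the regimen's overall safety profile is made to look better would go too far, because the absolute-threshold flags, observed values and AE listings are unaffected. The primary and secondary efficacy analyses and the power do not depend on any of this.

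**What to change.** 1. Keep the Day 1 procedure as the anchor for the main OAV101-versus-sham TEAE tables.
2. Start the prednisolone/placebo-related AE table at the first prednisolone/placebo dose, or add a by-arm table of AEs from that dose to the procedure. State its denominator, since the SAF covers only children who had the Period 1 procedure.
3. For crossovers, assign events and values from the first Period 2 prednisolone/placebo dose onward to Period 2, if that dose precedes the Week 52 + 1 Day procedure.
4. Add a blood-pressure change summary that uses the last value before the first prednisolone/placebo dose as baseline.
5. Align the TEAE wording in SAP 2.1.1 with the date rule in Protocol 12.5.2, so that an event on Day 1 before the injection is classified one way.

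The cost is SAP wording, one date variable and one or two extra outputs. AEs are already collected from consent, and home doses and their dates are recorded in the diary. No change to conduct is needed.

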2.1.2 Analysis visit windows

Unless otherwise specified, **analysis visit windows** for efficacy and safety assessments which are summarized on a by-visit basis are defined based on study day post dosing. For by-visit endpoints, the time windows describe how data will be assigned to protocol-specified time points during follow up.

Period 2 windows defined below will be used for analyses of “on or after OAV101 administration” (i.e., OAS).

The analysis windows for respective assessments are as follows:

Vital Signs and Neurological Examination:

Period 1 windows:

Visit	Nominal day	Start day	End day
Day 1	Day 1	Day 1	Day 1
Day 2	Day 2	Day 2	Day 2
Day 3	Day 3	Day 3	Day 3
Week 1	Day 8	Day 4	Day 11
Week 2	Day 15	Day 12	Day 18
Week 3	Day 22	Day 19	Day 25
Week 4	Day 29	Day 26	Day 36
Week 6	Day 43	Day 37	Day 50
Week 8	Day 57	Day 51	Day 64

Visit	Nominal day	Start day	End day
Week 10	Day 71	Day 65	Day 78
Week 12	Day 85	Day 79	Day 99
Week 16	Day 113	Day 100	Day 127
Week 20	Day 141	Day 128	Day 155
Week 24	Day 169	Day 156	Day 183
Week 28	Day 197	Day 184	Day 211
Week 32	Day 225	Day 212	Day 239
Week 36	Day 253	Day 240	Day 267
Week 40	Day 281	Day 268	Day 295
Week 44	Day 309	Day 296	Day 323
Week 48	Day 337	Day 324	Day 351
Week 52	Day 365	Day 352	Week 52 + Day 1 – 1

Period 2 windows:

Visit (OAV-SHAM)	Visit (SHAM-OAV)	Nominal day	Start day	End day
Week 52 + Day 1	Day 1	Day 1	Day 1	Day 1
Week 52 + Day 2	Day 2	Day 2	Day 2	Day 2
Week 52 + Day 3	Day 3	Day 3	Day 3	Day 3
Week 53	Week 1	Day 8	Day 4	Day 11
Week 54	Week 2	Day 15	Day 12	Day 18
Week 55	Week 3	Day 22	Day 19	Day 25
Week 56	Week 4	Day 29	Day 26	Day 36
Week 58	Week 6	Day 43	Day 37	Day 50
Week 60	Week 8	Day 57	Day 51	Day 64
Week 62	Week 10	Day 71	Day 65	Day 78
Week 64	Week 12	Day 85	Day 79	Last participation day

Body Weight:

Period 1 windows:

Visit	Nominal day	Start day	End day
Day 1	Day 1	Day 1	Day 1
Day 2	Day 2	Day 2	Day 2
Week 1	Day 8	Day 3	Day 18

Visit	Nominal day	Start day	End day
Week 4	Day 29	Day 19	Day 43
Week 8	Day 57	Day 44	Day 71
Week 12	Day 85	Day 72	Day 99
Week 16	Day 113	Day 100	Day 127
Week 20	Day 141	Day 128	Day 155
Week 24	Day 169	Day 156	Day 183
Week 28	Day 197	Day 184	Day 211
Week 32	Day 225	Day 212	Day 239
Week 36	Day 253	Day 240	Day 267
Week 40	Day 281	Day 268	Day 295
Week 44	Day 309	Day 296	Day 323
Week 48	Day 337	Day 324	Day 351
Week 52	Day 365	Day 352	Week 52 + Day 1 – 1

Period 2 windows:

Visit (OAV- SHAM)	Visit (SHAM- OAV)	Nominal day	Start day	End day
Week 52 + Day 1	Day 1	Day 1	Day 1	Day 1
Week 52 + Day 2	Day 2	Day 2	Day 2	Day 2
Week 53	Week 1	Day 8	Day 3	Day 18
Week 56	Week 4	Day 29	Day 19	Day 43
Week 60	Week 8	Day 57	Day 44	Day 71
Week 64	Week 12	Day 85	Day 72	Last participation day

Body Height (Segmental by Tibial Length) and BMI:

Period 1 windows:

Visit	Nominal day	Start day	End day
Week 4	Day 29	Day 1	Day 43
Week 8	Day 57	Day 44	Day 71
Week 12	Day 85	Day 72	Day 127
Week 24	Day 169	Day 128	Day 211
Week 36	Day 253	Day 212	Day 295
Week 48	Day 337	Day 296	Day 351
Week 52	Day 365	Day 352	Week 52 + Day 1 – 1

Period 2 windows:

Visit (OAV-SHAM)	Visit (SHAM-OAV)	Nominal day	Start day	End day
Week 56	Week 4	Day 29	Day 1	Day 43
Week 60	Week 8	Day 57	Day 44	Day 71
Week 64	Week 12	Day 85	Day 72	Last participation day

Hematology and Clinical Chemistry:

Period 1 windows:

Visit	Nominal day	Start day	End day
Week 1	Day 8	Day 1	Day 11
Week 2	Day 15	Day 12	Day 18
Week 3	Day 22	Day 19	Day 25
Week 4	Day 29	Day 26	Day 36
Week 6	Day 43	Day 37	Day 50
Week 8	Day 57	Day 51	Day 64
Week 10	Day 71	Day 65	Day 78
Week 12	Day 85	Day 79	Day 99
Week 16	Day 113	Day 100	Day 127
Week 20	Day 141	Day 128	Day 155
Week 24	Day 169	Day 156	Day 183
Week 28	Day 197	Day 184	Day 211
Week 32	Day 225	Day 212	Day 239
Week 36	Day 253	Day 240	Day 267
Week 40	Day 281	Day 268	Day 295
Week 44	Day 309	Day 296	Day 323
Week 48	Day 337	Day 324	Day 351
Week 52	Day 365	Day 352	Week 52 + Day 1 – 1

Period 2 windows:

Visit (OAV-SHAM)	Visit (SHAM-OAV)	Nominal day	Start day	End day
Week 53	Week 1	Day 8	Day 1	Day 11
Week 54	Week 2	Day 15	Day 12	Day 18
Week 55	Week 3	Day 22	Day 19	Day 25
Week 56	Week 4	Day 29	Day 26	Day 36

Visit (OAV-SHAM)	Visit (SHAM-OAV)	Nominal day	Start day	End day
Week 58	Week 6	Day 43	Day 37	Day 50
Week 60	Week 8	Day 57	Day 51	Day 64
Week 62	Week 10	Day 71	Day 65	Day 78
Week 64	Week 12	Day 85	Day 79	Last participation day

HFMSE, RULM CCI : [REDACTED]

Period 1 windows:

Visit	Nominal day	Start day	End day
Week 4	Day 29	Day 1	Day 43
Week 8	Day 57	Day 44	Day 71
Week 12	Day 85	Day 72	Day 99
Week 16	Day 113	Day 100	Day 127
Week 20	Day 141	Day 128	Day 155
Week 24	Day 169	Day 156	Day 183
Week 28	Day 197	Day 184	Day 211
Week 32	Day 225	Day 212	Day 239
Week 36	Day 253	Day 240	Day 267
Week 40	Day 281	Day 268	Day 295
Week 44	Day 309	Day 296	Day 323
Week 48	Day 337	Day 324	Day 351
Week 52	Day 365	Day 352	Week 52 + Day 1 – 1

[figure not shown]
Period 2 windows:

Visit (OAV-SHAM)	Visit (SHAM-OAV)	Nominal day	Start day	End day
Week 56	Week 4	Day 29	Day 1	Day 43
Week 60	Week 8	Day 57	Day 44	Day 71
Week 64	Week 12	Day 85	Day 72	Last participation day

CCI [REDACTED]

CCI [REDACTED]

[figure not shown]
CCI

CCI

CCI

CCI

CCI

CCI

Troponin-I, Echocardiogram and ECG:

Period 1 windows:

Visit	Nominal day	Start day	End day
Week 1	Day 8	Day 1	Day 18
Week 4	Day 29	Day 19	Day 43
Week 8	Day 57	Day 44	Day 71
Week 12	Day 85	Day 72	Day 127
Week 24	Day 169	Day 128	Day 253
Week 48	Day 337	Day 254	Day 351 [#]
Week 52*	Day 365	Day 352	Week 52 + Day 1 – 1

* Only applicable for ECG

For troponin-I and echocardiogram, the end day for Week 48 will be Week 52 + Day 1 – 1 instead of 351

Period 2 windows:

Visit (OAV-SHAM)	Visit (SHAM-OAV)	Nominal day	Start day	End day
Week 53	Week 1	Day 8	Day 1	Day 18
Week 56	Week 4	Day 29	Day 19	Day 43
Week 60	Week 8	Day 57	Day 44	Day 71
Week 64	Week 12	Day 85	Day 72	Last participation day

If more than one observation is included in a time window for HFMSE and RULM, irrespective of the observations being scheduled or unscheduled, the latest observation will be used in analyses.

For other endpoints, when an assessment value for both a scheduled visit and an unscheduled visit are present within the same analysis window, the scheduled visit value will be used. Unscheduled visit data will only be used when there is no measurement from the scheduled visit in the defined window.

If more than one scheduled observation for a specific assessment is included in a time window, the assessment closer to the nominal time will be used. If there are two scheduled observations equally distant to the nominal time, the latest one will be used in analyses.

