8.4.1.2 Hematology

Hematology analysis will include a complete blood count with differential and platelet count. Samples will be collected and shipped in accordance with the laboratory manual provided by the central laboratory. Blood samples for hematology analysis will be collected as specified in the [Table 8-1](#).

Hematology analysis will include the following at all trial visits:

- Hematocrit
- Hemoglobin
- MCH
- MCHC
- MCV
- Platelets
- Red blood cells
- White blood cells
- Differential (Basophils, Eosinophils, Lymphocytes, Monocytes, Neutrophils, Bands)

Transient decreases in platelet counts, some of which met the criteria for thrombocytopenia, were observed in OAV101 clinical studies with intravenous administration. In most cases, the lowest platelet value occurred the first week following OAV101 administration. Platelet counts should be obtained before OAV101/sham administration and should be closely monitored in the first two weeks following treatment on a regular basis afterwards as specified in [Table 8-1](#), until any abnormal platelet counts return to baseline.

Hematology analyses are required prior to discharge on Day 2 and Week 52+2 Days. These tests will be performed as per investigational site standard procedures at the local laboratory. As determined by the Investigator, further hematology tests should be done in the first two weeks following OAV101 administration as per investigational site standard procedures at the local laboratory. Local labs should be entered on the respective eCRF page.

Investigators will receive hematology results from all other study visits from the central laboratory.

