2.7.3 Laboratory data

Safety laboratory data and genetic diagnosis laboratory data analyzed by both the central laboratory as well as by local labs will be utilized for safety analyses. The SAF will be used for all summaries of data.

Values at each scheduled visit as well as change from baseline values to each post-baseline visit through the end of Follow-up Period 1 will be summarized for each protocol-specified chemistry, hematology, and liver function test laboratory parameter using descriptive statistics for Treatment Period 1 treatment group (OAV101, sham). Normalized values (observed absolute values/ULN) for ALT, AST, ALP, total bilirubin and troponin-I and absolute values for platelets at each scheduled visit as well as change from baseline in absolute values to each post-baseline visit through the end of Follow-up Period 1 will be visualized on a box plot. Listings of hematology (all platelet values and out of range values for all other parameters), chemistry (out of range values for all parameters), urinalysis (out of range values for all parameters), and hepatic laboratory data meeting elevation criteria data will also be produced. Listings of liver imaging, if performed will also be produced.

In addition, shift tables based on CTC grade (CTCAE version 5) will be provided for all laboratory parameters that were defined in the [\[Novartis Internal Guidance on CTCR Grading of Lab Parameter\]](#) (e.g., platelets, alanine aminotransferase (ALT), aspartate aminotransferase (AST), alkaline phosphatase (ALP), gamma glutamyl transferase, and serum total bilirubin, etc.) to compare a participant's baseline laboratory evaluation relative to the post-baseline values. For laboratory (serum) parameters Glutamate Dehydrogenase and Troponin I, shift tables will be produced by below, within, or above the normal range level based on normal ranges of the laboratory used in this study (Low/Normal/High).

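### SAP 2.1.2 has no Day 2 hematology window, so the required Day 2 platelet count drops out of the by-visit outputs; Day 1 vital signs lose only their within-day course

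*SAP*

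**What the plan says.** **Protocol.** Section 8.4.1.2 makes an early count compulsory: "Hematology analyses are required prior to discharge on Day 2 and Week 52+2 Days". The local laboratory does it. Further local counts in the first two weeks are left to the investigator. The reason for watching this period is given in the same section: "In most cases, the lowest platelet value occurred the first week following OAV101 administration". The sentence before it limits that experience to intravenous dosing. On reporting, Section 12.5.2 says "All vital signs data will be summarized by treatment and visit/time" and uses parallel wording for laboratory data.

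**SAP.** The windows in 2.1.2 govern efficacy and safety assessments "which are summarized on a by-visit basis". The first hematology and chemistry row reads "Week 1 Day 8 Day 1 Day 11" (visit, nominal day, start, end). Vital signs have one-day rows for Days 1, 2 and 3, and body weight has rows for Days 1 and 2. Outside HFMSE and RULM, unscheduled values are used only if the window holds no scheduled one. Among scheduled values, "the assessment closer to the nominal time will be used", and "If there are two scheduled observations equally distant to the nominal time, the latest one will be used in analyses".

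Section 2.7.3 plans descriptive summaries and changes from baseline by visit, box plots of "absolute values for platelets at each scheduled visit", and shifts to each visit. Separately, it plans shifts to the worst CTC grade at any time after baseline and a listing of every platelet value. It uses both central and local results.

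**The concern.** Transient thrombocytopenia is an adverse event of special interest, and change from baseline in hematology is a secondary safety endpoint. The protocol obliges each site to take a Day 2 count, yet the windowing rules give that count no place in the outputs that show how platelets move over time in each arm. The planned platelet curve would in practice start at about Day 8.

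The omission looks inadvertent, because two other assessments do have a Day 2 row and 2.7.3 accepts local results.

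A smaller version of the problem affects vital signs on the dosing day. The protocol schedules close readings for 16 hours, and the by-visit table keeps one post-dose value.

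At stake is the clarity of the early safety comparison. No efficacy endpoint, error rate or power figure is involved.

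**Working it through.** The plan states no figure on this point, so there is nothing to reproduce. The check applies the SAP 2.1.2 rules to the protocol's schedule.

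**Platelets.** Distance = |study day − 8|.
- Day 2 count: |2 − 8| = 6.
- Week 1 visit in its protocol window (Day 8 ± 2, so Days 6 to 10): 0 to 2.
- Any other value on Days 3 to 11: at most |3 − 8| = 5.

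Treated as scheduled, Day 2 loses to any other scheduled value on Days 3 to 11. Treated as unscheduled, it loses to any scheduled value in the window. It survives only when no scheduled Week 1 value exists, and is then labelled Week 1. Extra local counts on Days 3 to 7 lose in the same way if they are classed as unscheduled.

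**Vital signs, dosing day.** From protocol 8.4.4, the post-dose readings other than blood pressure number 4 (hour 1) + 2 (to 2 h) + 3 (4, 6, 8 h) + 2 (12, 16 h) = 11. Blood pressure has 2 (8 h and 16 h). The SAP defines no time points within Day 1, so all readings on that date tie and the latest is kept. Which one that is depends on the clock time of dosing. The documents do not give it, so a range is assumed:

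| Assumed dosing time | Post-dose readings dated Day 1 | Kept | Dropped from Day 1 row |
|---|---|---|---|
| 07:30 | 11 | 16 h | 10 |
| 08:00 to 10:00 | 10 | 12 h | 9 |
| 12:00 to 14:00 | 9 | 8 h | 8 |
| 16:00 | 8 | 6 h | 7 |

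For blood pressure, the Day 1 row loses one post-dose reading with dosing at 07:30 and none from 08:00 to 14:00. At 16:00 no post-dose blood pressure falls on Day 1. Readings after midnight enter the Day 2 window, where the 20 to 24 hour reading displaces them. The pre-dose reading is not lost, because it serves as baseline under SAP 2.1.1.

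**Declared changes.** SAP Section 1 says substantial departures from the protocol will be identified. Section 4 lists two, and neither concerns windows or time points.

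**The case against.** The strongest reply is that no early value is lost to safety review. The worst-grade shift table and the listing of all platelet values do not depend on windows. Transient thrombocytopenia is tabulated by arm as an event of special interest, and SAP 2.7.1 tabulates events within 72 hours of treatment by arm. SAP 2.7.4.2 counts participants who ever meet a clinically significant vital-sign criterion. This stands. A reader might infer from the windows that the acute period is not summarized over time at all, and the documents do not support that. Vital signs have rows for Days 1, 2, 3 and Week 1, and only the course within Day 1 disappears.

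Three further points also stand:
- The statement about the platelet low comes from intravenous studies. The readable text does not establish its timing after intrathecal dosing or place it at Day 2.
- Keeping investigator-triggered counts out of the by-visit tables is defensible. Comparing arms on minima over all values would favour lower minima in whichever arm is sampled more.
- The by-visit laboratory outputs named in 2.7.3 run only through Follow-up Period 1, so the Period 2 effect is limited.

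It is also arguable that the protocol's slash means visit or time, which makes an undeclared change less than certain.

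None of this answers the platelet point. Grade shifts are threshold categories: they show neither the size nor the day of a fall, nor a fall that crosses no threshold. A listing is not a comparison between arms.

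**Conclusion.** The concern holds as a cheap, specific improvement. Whenever a scheduled Week 1 count exists, the compulsory Day 2 platelet count is removed from the by-visit summaries, box plots and by-visit shifts. With planned enrolment, that is up to about 125 children in Period 1 (about 75 OAV101, 50 sham). It remains in the worst-grade shifts and the listing, which do not show the size or timing of early falls by arm.

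For vital signs the loss is confined to the within-Day-1 course: 7 to 10 post-dose readings drop from the Day 1 row over the assumed dosing times, and at most one for blood pressure.

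Two assumptions matter. The hematology rows of protocol Table 8-1 are not readable, so the Day 2 requirement rests on Section 8.4.1.2. The SAP's nominal time is read as nominal day, since no within-day times are given.

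**What to change.** 1. In SAP 2.1.2, add a Day 2 row to the Period 1 hematology windows, for example Days 2 to 4 with Week 1 starting on Day 5. The whole protocol window for the Week 1 visit (Days 6 to 10) then stays in Week 1. State where any Day 1 post-dose sample goes. Add the matching Week 52+2 Days row to the Period 2 windows, which serve the OAV101 Treated Analysis Set.
2. In SAP 2.7.4.2, summarize Day 1 and Week 52+1 Day vital signs by the protocol's planned time points. Otherwise, declare the narrowing to one value per visit in Section 4.
3. If minimum platelet count and maximum fall by arm are added to 2.7.3, base the between-arm comparison on scheduled samples (Day 2, Week 1, Week 2). Show an all-values version only descriptively, because the extra local counts are discretionary.

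The cost is SAP wording and a few table rows from data already collected. The drawback is that Day 2 values are local and later ones central, a mix the SAP already accepts for safety analyses.
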